#### PREOPERATIVE PROCEDURES

- Informed consent documentation
- General medical and ocular history
- Ocular and systemic medications
- Contact lens trial
- Inclusion/exclusion criteria
- PRSVQ Questionnaire
- iDesign System Measurement (refraction, aberrometry, topography, keratometry, pupillometry)
- UCDVA
- Manifest Refraction
- BSCVA
- BSCVA – low contrast (10%)
- Minimum add power
- DCIVA
- DCNVA
- Keratometry (auto or manual)
- Corneal topography
- Anterior segment examination (biomicroscopic slit-lam exam)
- Intraocular pressure (applanation tonometry)
- Pachymetry
- Cycloplegic Refraction
- Dilated fundus examination
- iDesign treatment planning
- Adverse events (Ocular/NonOcular)

- Device deficiencies/complaints
- Refractive stability

#### 10.4 CONTACT LENS STUDY

All subjects will be required to undergo a contact lens trial to simulate their intended correction for a minimum of 7 days. This will involve wearing a multifocal contact lens in the non-dominant eye and a single vision distance contact lens in the dominant eye. Subjects will provide responses on a questionnaire to indicate their level of satisfaction with the simulated correction (refer to Appendix P).

Subjects must indicate “**Very Satisfied**”, “**Satisfied**”, or “**Somewhat Satisfied**” with their vision for all of the following in order to successfully complete the contact lens study:

• Driving during daylight	• Driving at night
• Working on the computer	• Overall experience

Upon successful completion of the contact lens study, subjects will be instructed to remove their contact lenses for a minimum of two weeks prior to surgery.

#### 10.5 OPERATIVE PROCEDURES

Both eyes of the subject may be treated at the same visit. However, if an epithelial defect is present on the flap of the first eye, or if a clinically significant complication or adverse event is observed during the treatment of the first eye, the fellow eye will not be treated until resolution of the event in the first eye.

To ensure control of environmental conditions during treatments, including temperature and humidity, all laser suites shall be equipped with air conditioning and/or heating systems, humidifiers, and environmental monitoring devices. It is important to maintain a carefully controlled surgical environment. All treatments shall be performed in surgical environments where the humidity is between 35-45% and the temperature is between 68-72° F.

All eyes will undergo the LASIK procedure using the IntraLase® Femtosecond laser to perform the initial lamellar cuts and the STAR SR IR™ Excimer laser to perform ablation according to the iDesign-derived treatment plan. Iris Registration (IR) should be used for alignment of all treatments. Following treatment, the use of a bandage contact lens will be at the discretion of the investigator. Refer to **Appendix N** for a detailed summary of the surgical procedure.

## 10.6 POSTOPERATIVE PROCEDURES

Postoperatively, each treated eye will be examined according to the schedule in Section 10.2, Visit Schedule.

### IMMEDIATE POSTOPERATIVE CARE

Subjects may experience pain during the first 24 hours following treatment. The immediate postoperative pain control regimen is left to the Investigator's discretion. All postoperative regimen components shall be recorded. Prescribe the following postoperative regimen and instruct the subject to return the next day:

- Eye shield(s) during sleep (1 week)
- Topical ophthalmic antibiotic: QID for at least 4 days
- Topical ophthalmic corticosteroid: QID for at least 4 days (but should not be prescribed QID for more than 7 days unless medically warranted)

### EARLY POSTOPERATIVE EXAMINATION PROCEDURES (1 DAY AND 1 WEEK)

Postoperative examinations will be conducted at 1 day and 1 week after treatment. The following clinical information shall be assessed and recorded for both eyes during each postoperative exam (see also **Appendix A**). General descriptions and requirements of tests are provided in **Appendix C**.

- Ocular and systemic medical history and concomitant medications
- iDesign System Measurement (refraction, aberrometry, topography, keratometry, pupilometry), (not required at 1-day exam)
- UCDVA
- Manifest Refraction (not required at 1-day exam)
- BSCVA (not required at 1-day exam)
- Keratometry (not required at 1-day exam)
- Anterior Segment Examination
- Adverse Events and Complications
- Device Deficiencies/Complaints

### PERIODIC POSTOPERATIVE EXAMINATION PROCEDURES

Periodic examinations will be conducted at 1, 3, 6, and 9 months after treatment. In the event that extended follow-up is not needed, the follow-up period may be reduced.

Note: Subjects are not to wear contact lenses postoperatively until after completion of this study. Wearing contact lenses may potentially cause corneal edema or topography

changes that may influence the visual acuity results. During the study, if correction is required, spectacles should be prescribed.

The following data shall be assessed and recorded for both eyes during the periodic examinations, although not all are required at all periodic visits (see also **Appendix A**). General descriptions and requirements of the various tests are provided in **Appendix C**.

- Ocular and systemic medical history and concomitant medications
- PRVSQ Questionnaire (1, 3, 6, and 9 month visit)
- iDesign System Measurement (refraction, aberrometry, topography, keratometry, pupillometry)
- UCDVA, photopic, monocular
- UCDVA, photopic, binocular
- Manifest Refraction (logMAR)
- BSCVA, photopic, monocular, distance (logMAR)
  - At 3 months or later, if there is a loss of 2 or more lines of BSCVA ( $\geq 10$  letters) compared to the preoperative visit, a rigid contact lens over refraction should be performed to estimate the best possible corrected visual acuity. If a rigid contact lens over refraction is not medically advisable, then a pin-hole acuity should be obtained
- BSCVA, photopic, binocular, distance (logMAR) (3, 6, and 9 month visit)
- BSCVA, photopic, monocular, distance low contrast, 10%, (logMAR) (3, 6, and 9 month visit)
- DCNVA, mesopic, monocular at 40 cm (3, 6, and 9 month visit)
- Pupil size
  - Mesopic, distance and near (3 month visit)
  - Photopic, distance and near (3 month visit)
- DCIVA, photopic, monocular (3, 6, and 9 month visit)
- DCIVA, photopic, binocular (3, 6, and 9 month visit)
- DCNVA, photopic, monocular (3, 6, and 9 month visit)
- DCNVA, photopic, binocular (3, 6, and 9 month visit)
- UCIVA, photopic, monocular (3, 6, and 9 month visit)
- UCIVA, photopic, binocular (3, 6, and 9 month visit)
- UCNVA, photopic, monocular (3, 6, and 9 month visit)
- UCNVA, photopic, binocular (3, 6, and 9 month visit)
- Defocus curve testing (3, 6, and 9 month visit)
- Anterior Segment Examination

- Pachymetry (6 month exam)
- Auto or Manual Keratometry
- Corneal Topography
- Cycloplegic Refraction (6 month exam)
- Dilated fundus exam (6 month exam)
- Adverse Events and Complications
- Device Deficiencies/Complaints

## **10.7 RETREATMENT PROCEDURES**

### NON-REFRACTIVE RETREATMENTS

Non-refractive retreatments or procedures without further laser treatment (e.g., flap lifts, adjustments, realignments, replacement, treatment of complications, removal of epithelial ingrowth) may be performed at any time with the advance notification of the Sponsor. All flap adjustment procedures will be noted and reported to the Sponsor.

### REFRACTIVE RETREATMENTS

There will be no refractive retreatments in this study.

## **10.8 EXIT OF SUBJECTS**

An Exit Case Report Form will be completed for all subjects, either when they complete the study or if they exit early.

It is the responsibility of the investigator to provide complete follow-up data to AMO for each subject, and every attempt should be made to gather that complete follow-up data for all subjects enrolled as missing data can have a negative effect on the study results. Patients who would be traveling, relocating or otherwise unavailable for postoperative follow-up visits should not be chosen for this clinical study.

Subjects will be discontinued from the study if the subject dies. Subjects will be considered “lost-to-follow-up” from the study only if irretrievably lost for unavoidable reasons such as: subject moved/unable to locate, subject uncooperative/refuses further study participation, subject ill/unable to travel. In the event of subject relocation, efforts must be made by the investigator to secure follow-up information (i.e., slit-lamp findings and general visual acuity, etc.) from the subject’s new physician.

If a subject is exited early from the study, the investigator will complete an Exit Case Report Form indicating the reason for study exit. In the event of a serious adverse event, the subject may be exited from the study; however, efforts must be made by the investigator to follow the subject until resolution of the adverse event.

Additionally, all study subjects are to be instructed to undergo regular eye examinations at least yearly and also to return to their doctor if any eye complications are experienced in the interim.

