#### **Serious Adverse Event (SAE)**

An adverse event is considered serious (following ISO 14155) if it is an untoward occurrence which may or may not be related to use of the study device that

- is sight- or life-threatening,
- results in death,
- requires inpatient hospitalization or prolongation of hospitalization (a planned hospitalization for a pre-existing condition is not considered a serious adverse event),
- results in permanent impairment of a body structure or body function,
- necessitates medical or surgical intervention to prevent permanent impairment to a body structure or function, or
- results in fetal distress, fetal death or a congenital abnormality or birth defect

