#### **11.5 ADVERSE EVENT FOLLOW-UP**

For every adverse event, appropriate measures should be undertaken to treat and/or monitor the subject until resolution occurs. Obtain and maintain in the subject's files all

pertinent medical data relating to the event including the subject's medical records and medical reports and/or judgments from colleagues or outside specialists who assisted in the treatment and follow-up of the subject. The investigator should keep AMO closely informed as to the outcome of serious and/or device-related adverse events, thereby allowing AMO to comply with the appropriate regulatory reporting requirements. A Serious and/or Device-Related Adverse Event Update CRF should be completed each time the subject returns to the investigator or other specialist(s) for follow-up of serious and/or device-related adverse event until resolution of the event. Any subject who is exited from the study due to a serious and/or device-related adverse event will be followed until the outcome is determined.

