## **19. TERMINATION OF THE INVESTIGATION**

The clinical investigation will be suspended in the event of high levels of complications and/or adverse events that are unexpected in nature and/or severity and evaluated as to causality relative to the study device. The clinical investigation may be suspended if the Medical Monitor or IRB, upon review and evaluation of the clinical data, finds unacceptable clinical performance or the level of single or total complications and/or adverse events unacceptable for continuation of the investigation.

If causality is shown not to be related to the study device, the study may be resumed in accordance with the IRB and regulations of Health Canada and governing countries. The study will be terminated if causality is shown to be related to the study device.

Additionally, the investigator, or AMO, may stop a subject's participation at any time. AMO may also stop the study at any time for reasons it determines appropriate. However, no suspension of the study would be made to disadvantage the study subjects. Following suspension of the study for any reason, all study subjects who have already received treatment would continue to be followed through completion of the study visit schedule.

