## **Safety Endpoints**

### MONOCULAR BSCVA

Mean monocular BSCVA will be reported by test and control groups with the mean difference between postoperative and preoperative BSCVA evaluated using a two-sided, 90% confidence interval (CI). The null hypothesis is that the mean difference (postoperative minus preoperative) in logMAR BSCVA is greater than or equal to 0.1 logMAR. The alternative hypothesis is that the mean difference in BSCVA is less than 0.1 logMAR.

$H_0: \mu_{\text{diff}} \geq 0.1$

$H_1: \mu_{\text{diff}} < 0.1$

where

$\mu_{\text{diff}}$  = the mean difference in logMAR BSCVA between postoperative and preoperative eyes (postoperative minus preoperative).

The success criterion is achieved if the upper limit of the 90% CI of the differences in mean logMAR BSCVA for postoperative compared to preoperative eyes is < 0.1 logMAR for both test and control groups.

Clinical significance is achieved if the mean postoperative BSCVA is no more than one line worse than preoperative BSCVA for both test and control groups.

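### A treated subject may be exited after a serious adverse event with no 6-month acuity required, which can tilt the BSCVA safety test toward a pass

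*Protocol*

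**What the plan says.** Protocol Section 10.8 allows exit for harm: "In the event of a serious adverse event, the subject may be exited from the study". The same sentence goes on to say that "efforts must be made by the investigator to follow the subject until resolution of the adverse event". Section 11.5 adds: "Any subject who is exited from the study due to a serious and/or device-related adverse event will be followed until the outcome is determined". The definition of a serious event in Section 11.1 includes one that "is sight- or life-threatening", as well as permanent impairment and non-ocular hospitalisation.

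Section 19 gives a second route out: "the investigator, or AMO, may stop a subject's participation at any time". Full follow-up after treatment is promised there only if the study is suspended, when "all study subjects who have already received treatment would continue to be followed through completion of the study visit schedule".

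All endpoints are evaluated at 6 months, and the analysis population is every treated eye (Protocol 20.1, SAP 2.1). The BSCVA criterion (Protocol 20.2, SAP 3.5) needs the upper limit of the 90% interval for the mean postoperative-minus-preoperative change to lie below 0.1 logMAR "for both test and control groups". Induced astigmatism and adverse events are only summarised. SAP 2.2 and 3.1 report how many eyes are missing. The SAP has no imputation rule and no sensitivity analysis.

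**The concern.** Once both eyes have been ablated, leaving the study ends measurement, not exposure. What follows exit is tied to the event: it can close before month 6, and it names no acuity test. An exited eye stays in the stated population but has no 6-month value to enter the interval.

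The permission is triggered by harm, so the missing eyes may be the ones with the worst vision. For BSCVA the bias then runs one way, toward a pass. Exit is by subject, so the pair also leaves the DCIVA and DCNVA paired t-tests. The study is open-label, so whoever decides on exit knows which treatment each eye received.

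**Working it through.** **The plan's own figure.** Sample size section: 34 subjects, difference 0.7 line, SD 1.4 lines, two-sided alpha 0.05. The noncentrality is (0.7/1.4) × √34 = 2.915 on 33 df, which gives power 80.8% and agrees with the stated figure of over 80%. The one-sided 0.025 test gives the same value. With 33 pairs power is 79.5%, and with 32 it is 78.2%. This loss applies only if 34 is the number treated. The synopsis reads that way, while Section 8 asks for at least 34 at 6 months.

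**BSCVA interval: inputs.** The margin (0.1), the 90% interval and n = 34 come from the documents. The SD of the change, the mean change in the other eyes and the size of loss do not. I assume SD 0.10 logMAR (range 0.07 to 0.14), means of 0.00 to +0.05, and losses of 0.3, 0.5 or 1.0.

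**Formulas.** Upper limit U = m + t(0.95, n−1) × SD/√n. When k eyes with change L join r eyes with mean m0 and SD s, and n = r + k:
- m = (r·m0 + k·L)/n
- SD² = [(r−1)s² + (rk/n)(L−m0)²]/(n−1)

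**Worked case.** r = 33, m0 = 0.02, s = 0.10, k = 1, L = 1.0.
- Without the eye: 0.02 + 1.6939 × 0.10/√33 = 0.0495, a pass.
- With it: m = (0.66 + 1.00)/34 = 0.0488.
- SD = √[(0.320 + 0.932)/33] = 0.1948.
- U = 0.0488 + 1.6924 × 0.1948/√34 = 0.1054, a fail.

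**Range.** Every limit without the exited eyes is below 0.1 for all three SDs.

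| Exited eyes | Mean of the rest | U without, SD 0.10 | U with, SD 0.07 | U with, SD 0.10 | U with, SD 0.14 |
|---|---|---|---|---|---|
| 1 losing 1.0 | 0.00 | 0.0295 | 0.0831 | 0.0868 | 0.0933 |
| 1 losing 1.0 | 0.01 | 0.0395 | 0.0923 | 0.0961 | 0.1026 |
| 1 losing 1.0 | 0.02 | 0.0495 | 0.1015 | 0.1054 | 0.1119 |
| 1 losing 1.0 | 0.05 | 0.0795 | 0.1293 | 0.1332 | 0.1399 |
| 2 losing 0.5 | 0.02 | 0.0500 | 0.0869 | 0.0918 | 0.0998 |
| 2 losing 0.5 | 0.03 | 0.0600 | 0.0957 | 0.1007 | 0.1088 |
| 2 losing 0.5 | 0.05 | 0.0800 | 0.1134 | 0.1185 | 0.1267 |
| 1 losing 0.5 | 0.05 | 0.0795 | 0.0933 | 0.0995 | 0.1091 |
| 2 losing 0.3 | 0.05 | 0.0800 | 0.0909 | 0.0977 | 0.1077 |
| 1 losing 0.3 | 0.00 | 0.0295 | 0.0338 | 0.0411 | 0.0515 |

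**Efficacy.** Suppose 33 pairs average a 0.10 logMAR benefit, which is the one-line criterion. If the missing pair has a test eye 0.3 worse than its control, the all-treated mean is (33 × 0.10 − 0.3)/34 = 0.088, and the loss of the pair flatters the result. If the control eye is the one 0.3 worse, the mean is (33 × 0.10 + 0.3)/34 = 0.106, and the loss understates it.

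**The case against.** Several things speak for the plan. Exit is optional. Section 10.8 also makes the investigator responsible for complete follow-up data and asks for every attempt to obtain it, and Section 15.1 adds steps to prevent missing data. A visual event that persists can keep adverse event follow-up open past 6 months, and corrected acuity may be recorded at unscheduled visits. The harm is not hidden: serious and device-related events are counted and listed, missing eyes are tabulated, and the Medical Monitor reviews each serious event. Many such events may be non-ocular. What is exposed is one mean-based criterion in a feasibility study, and it takes severe loss to reverse it. All of this stands and limits the size of the point. None of it secures the 6-month acuities of a treated subject who has been exited.

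A reader might infer more than the documents support:
- **That exit never prevents exposure.** Section 10.5 defers the fellow eye until a first-eye event resolves, so exit in that interval can prevent a treatment. Adverse events are also collected from consent onward, including during the contact lens trial, when exit costs no 6-month data from a treated eye.
- **That Section 19 contradicts itself or Section 10.8.** Suspension of the study and the stopping of one subject are different situations, and different rules for them are not a contradiction.
- **That these exits fit no accountability category.** Section 10.8 says death leads to discontinuation, not that only death does. SAP 3.1 has a general discontinued category, and the Exit CRF records the reason.
- **That efficacy is inflated.** The direction depends on which eye is harmed, and a non-ocular event has no evident direction.

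**Conclusion.** The concern holds for subjects treated in at least one eye. The plan allows exit because of harm, does not require the 6-month acuities afterwards, and has no analysis for the eyes that are then missing. The BSCVA interval can be biased toward a pass; for the paired tests the direction is open.

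The size is conditional. At the assumed SD of 0.10, reversal needs one eye losing 1.0 logMAR with the rest averaging about +0.02 or more, or two eyes losing 0.5 with the rest at about +0.03 or more. One eye losing 0.5 does not reverse the result even at +0.05, where the limit is 0.0995, though at SD 0.14 it does. With the rest at a mean of zero, neither one eye losing 1.0 nor two losing 0.5 is enough. No event rate is given, so I put no probability on any of these cases. The change is worth making because it costs little and a safety test should not depend on who was kept in follow-up.

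**What to change.** **Protocol 10.8 and 19.** State that, for subjects who have received study treatment in at least one eye, neither an adverse event nor a decision to stop participation ends data collection. They are asked to stay on the Table 1 schedule, including monocular BSCVA, DCIVA and DCNVA at 6 months, unless they refuse or cannot attend. In that case these acuities are measured at the last visit if possible. Exit before any treatment is unaffected, and decisions about the fellow eye stay with the existing text.

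**SAP 3.5.** Add a sensitivity BSCVA interval. For treated eyes with no 6-month value, use the last available postoperative BSCVA, including unscheduled and adverse event follow-up visits. Note beside it that an early, transient loss may be carried forward, so this supports the main interval and does not replace it.

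**Cost.** A few sentences in the protocol, one more analysis row, and a few more visits for subjects who would otherwise have been exited.

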## **10.9 UNSCHEDULED VISITS**

During the study period, if a non-protocol-required visit is done for the purpose of medically-indicated follow-up for a study eye, data from this visit should be reported using the Unscheduled Visit CRF. The need for unscheduled visits is at the investigator's discretion. Specific examinations to be performed at unscheduled visits are also at the discretion of the investigator (based on the reason for the unscheduled visit) and data are to be recorded in the appropriate section of the case report form.

Data to be collected may include:

- Manifest refraction
- Uncorrected and best corrected distance visual acuity
- Intraocular pressure
- Anterior segment examination
- Dilated fundus exam
- Ocular symptoms
- Adverse events
- Medications

In addition, if a subject is seen at an Unscheduled visit due to an optical/visual symptom complaint, the PRO Visual Symptom Questionnaire will be administered at that visit, as well as prior to any secondary surgical intervention for an optical/visual symptom complaint. If additional unscheduled visits and/or a secondary surgical intervention due to the same optical/visual symptom complaint occur within 2 weeks of each other, it is not necessary to complete the PRO Visual Symptoms Questionnaire a second time.

## **10.10 PROTOCOL DEVIATIONS**

Any departure from the protocol procedures represents a protocol deviation. Protocol deviations may be subject-based (e.g., inclusion/exclusion criteria, informed consent deviation, etc.) or procedural-based (e.g., out-of-interval visits, non-compliance with testing procedures, etc.). All protocol deviations will be documented using protocol deviation case report forms. Any deviation made to protect the life or physical well-being of a subject in an emergency as well as any use of the investigational device without obtaining informed consent must be reported to AMO within 5 working days. Protocol deviations will be monitored by AMO, and if the non-compliance is persistent or egregious, AMO may take action, including but not limited to termination of the investigator's participation in the study. The investigator is also responsible for informing the reviewing IRB of instances of protocol non-compliance in accordance with the IRB requirements.

## 11. ADVERSE EVENTS AND PRODUCT COMPLAINTS

### 11.1 ADVERSE EVENT DEFINITIONS

#### **Adverse Event (AE)**

An adverse event is defined (following ISO 14155) as any untoward medical occurrence, unintended disease or injury, or untoward clinical signs (including abnormal laboratory findings) in subjects, users or other persons, whether or not related to the study device.

